- t. If the participant is intubated, endotracheal samples need to be taken at the same time as the NP swab. If taking both NP and endotracheal samples is not feasible, the NP sample should be given priority.

- u. Lab testing for detection of SARS-CoV-2 on the NP swab at day of hospital discharge. If SARS CoV-2 positive, an additional NP swab will be taken every 7 days, if feasible for the site and tested, until SARS-CoV-2 negative.
- v. If viral RNA is detected in NP samples at day of discharge, all possible efforts will be made to follow-up participants and collect samples every 7 days until viral RNA is negative, considering the current pandemic and related logistical challenges. If possible, home visits by a healthcare professional may be conducted to collect samples during the follow-up period.
- w. Includes serum samples for measurement of PK, antibodies to sirukumab, and IL-6. On Day 1, a predose and a postdose (within 30 minutes after the end of infusion) sample should be collected. The postdose sample should be collected from the arm contralateral to that used for IV infusion. On Day 1 (predose) and Day 28 the PK, antibodies to sirukumab, and IL-6 will be evaluated. On Day 1 (postdose), Day 14, and Day 21 the PK and IL-6 will be evaluated.
- x. PAXgene RNA tubes should always be used last for any blood draw.
- y. An optional pharmacogenetics blood sample (DNA) will be obtained from those participants who gave consent (where local regulations permit).
- z. Sample can be also taken at any other time point after study drug intervention on Day 1.
- aa. For those participants discharged prior to Day 28, all Day 28 assessments should be done at day of discharge. Laboratory, virology, relevant respiratory function related assessments, and biomarker/pharmacology assessments completed maximum 1 day before discharge do not need to be repeated on the day of discharge provided that no clinically relevant changes were noted in the results and the participant was declared 'ready to be discharged' on the day before discharge.
- bb. Assessments done at screening do not need to be repeated at baseline.
- cc. For participants still hospitalized post Day 28, additional blood sampling should be done every 7 days (± 1 day) and at day of discharge.
- dd. For all laboratory tests done on Day 21, Day 28, and every week thereafter as needed, a window of ± 1 day for all sampling is allowed.

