8.4.1. Evaluations

At visits where PK, immunogenicity, and IL-6 will be evaluated (Day 1 predose, Day 28), one venous blood draw will be collected as specified in the [Schedule of Activities \(SoA\)](#). Serum samples will be obtained and split into 3 aliquots (one for sirukumab concentration, one for antibodies to sirukumab, and one for IL-6).

At visits where PK and IL-6 will be evaluated (Day 1 postdose, Day 14, Day 21), one venous blood draw will be collected as specified in the [Schedule of Activities \(SoA\)](#). Serum samples will be obtained and split into 2 aliquots (one for sirukumab concentration and one for IL-6).

Additional information about the collection, handling, and shipment of biological samples can be found in the Laboratory Manual.

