| To evaluate immunogenicity following Sirukumab treatment | 
 Proportion of participants with Sirukumab antibodies (Day 28 or at discharge if discharged after Day 28) |
| To evaluate SARS-CoV-2 humoral immunity | 
 Serum levels of SARS-CoV-2 specific antibodies |

At the time of data analysis, additional endpoints may be considered for analysis in function of the evolution in scientific knowledge on COVID-19.

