2.2.7 Per-Protocol (PP) Analysis Set

The PP analysis set consists of participants in ITT analysis set who don't have any major protocol deviations that could have influenced the efficacy of Sirukumab during the study. This analysis set will be used for exploratory analysis of primary efficacy endpoint if more than 10% of ITT participants have major protocol deviations that could have influenced the efficacy evaluation.

2.3 Study Day 1

Study Day 1 refers to the day/date of the study drug administration (which is the same as the treatment phase start date).

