6.5 Analysis of Undetectability of Viral Load

For the analysis of undetectability of viral load all subjects with at least a post-baseline measurement of viral load by Nasopharynx assay will be considered.

For the primary analysis, all measurements of viral load up to Day 31 of the study (i.e. protocol window: Day 28+3 days) by the NP assay from central lab (central lab) will be used. Plots for individual participants will be generated using data up to Week 16.

Time (Days) to undetectability of virus load will be evaluated using the **First confirmed undetectability (CU)** approach as described below.

First confirmed undetectability (CU)

A participant is said to have (CU) of viral load if (1) participant has two consecutive undetectable viral loads, or (2) if the last viral load in the database is undetectable.

If there is at least one incidence of the CU then the date of the first undetectability among all CUs will be used to find the days from the study dose date to first CU of viral load. If there is no CU until study Day 31 then participant will be censored at date of last viral load assessment until study Day 31.

Following rules will be applied to derive the flags for event (of first CU) or censoring, and to derive the Days to event or censoring.

[For clarity, in the examples below of different cases a detectable viral load is denoted by 'D', and undetectable by 'U', and 'x' will represent any type of load (undetectable or detectable)].

(1) Case when a participant has only 1 viral load measurement in database (therefore it is also the last viral load measurement):

- a. If the viral load is undetectable then censor flag = No (same as Event = Yes) [example: U => censor flag = No],

Days to event = date of last viral load measurement – dose date + 1.

- b. Otherwise if the viral load is detectable then censor flag = Yes (same as Event = No),
[example: D => censor flag = Yes].

Days to censoring = date of last viral load assessment – dose date + 1.

(2) Case when a participant has more than 1 viral load measurements in the database:

- a. if there are no cases of 'CU cases based on 2 consecutive viral loads' then
 - i. if last viral load in the database is undetectable then

censor flag = No (same as Event = Yes),
 [example: U₁DDU₂DU₃DU₄ => censor flag = No],

ii.if last viral load in the database is detectable then
 censor flag = Yes (same as Event = No),
 [example: U₁DDU₂DU₃D => censor flag = Yes],

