8.3.2 Analysis Methods for Immunogenicity

Analysis of immunogenicity information will be performed using participants in IMG analysis set.

A participant is said to be positive for antibodies to Sirukumab if participant was positive for antibodies to Sirukumab at any time after Sirukumab administration until Day 28 of the study. A participant is classified as negative for antibodies to Sirukumab only if he/she was not positive at any time through Day 28 (that means participant must be negative for antibodies all through Day 28).

For participants who had 1 or more evaluable samples obtained after Sirukumab administration through study Day 28, a table showing number and percent of participants with positive results and negative results for antibodies to Sirukumab will be generated. Number of participants with peak titers will be shown in the table.

For Day 1 (pre- and post-dose), Day 14, 21 and 28 of the study, a table with summary statistics of serum Sirukumab concentrations (n, mean, SD, coefficient of variation, median, min and max) will be provided by participants with negative and positive for antibodies to Sirukumab.

A plot showing median and IQ range of serum Sirukumab concentrations over time by antibody status will be generated. Plots showing median and IQ range of serum Sirukumab concentrations over time by antibody status will be generated by the following subgroups:

- (1) Median and IQR over time by baseline Free IL-6 (ng/L) tertiles: <= 33%, > 33% and <= 66%, and > 66% percentiles at baseline), and
- (2) Median and IQR over time by baseline CRP (mg/L) tertiles: <= 33%, > 33% and <= 66%, and > 66% percentiles at baseline).

A listing of participants positive for antibodies to Sirukumab any time through Day 28 will be generated.

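### SAP 8.3.2 stops counting anti-sirukumab antibody samples at study Day 28, although the protocol allows the Day 28 draw on Day 29

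*SAP*

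**What the plan says.** **Analysis rule.** SAP 8.3.2 calls a participant positive if an antibody result is positive after dosing and no later than Day 28. The converse reads: "A participant is classified as negative for antibodies to Sirukumab only if he/she was not positive at any time through Day 28". The results table is introduced with "For participants who had 1 or more evaluable samples obtained after Sirukumab administration through study Day 28", and the listing of positives has the same limit. Study days follow the calendar: "Study Day 1 refers to the day/date of the study drug administration" (SAP 2.3).

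**Sampling.** Protocol 8.4.4, footnote w of the Schedule of Activities and SAP 8.1 schedule antibody samples only before dosing on Day 1 and on Day 28. Footnote dd, attached to the biomarker and pharmacology block that holds this sample, covers Day 28 laboratory tests: "a window of ± 1 day for all sampling is allowed".

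**Endpoint.** SAP 1.1 and Protocol 3 both define the exploratory endpoint; the SAP wording is "Proportion of participants with Sirukumab antibodies (Day 28 or at discharge if discharged after Day 28".

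**Neighbouring rules.** At the Day 28 visit one blood draw serves three purposes: "Serum samples will be obtained and split into 3 aliquots (one for sirukumab concentration, one for antibodies to sirukumab, and one for IL-6" (Protocol 8.4.1). SAP 7.2 assigns IL-6 results from study Days 26 to 30 to Day 28. SAP 6.5 uses viral load "up to Day 31 of the study (i.e. protocol window: Day 28+3 days". Neither section sets a window for anti-sirukumab antibodies.

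**The concern.** The sampling schedule and the analysis rule disagree about which days count as Day 28. A draw on Day 29 complies with the protocol, yet on its face SAP 8.3.2 ignores the antibody result from it. An inpatient has no second scheduled post-dose antibody sample to fall back on. The IL-6 aliquot from the same draw would still be analysed as Day 28.

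The SAP then also disagrees with itself and with the protocol. The immunogenicity set (SAP 2.2.6) accepts any valid post-dose sample, with no day limit. Protocol 9.4.7 bases the antibody incidence on participants who have a predose and a Day 28 sample, and a draw within the window is that sample. At stake are valid results already collected for the immunogenicity objective, and a defined antibody status in the tables and plots of sirukumab concentration.

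**Working it through.** The plan states no figure on this point, so there is none to reproduce. The check compares rules and then sizes the loss under stated assumptions.

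**Step 1: permitted days against counted days.** Footnote dd gives 28 − 1, 28 and 28 + 1, that is Days 27, 28 and 29. A limit at study Day 28 keeps Days 27 and 28 and drops Day 29.

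**Step 2: who can be affected.**
- Discharged before Day 28: the Day 28 assessments are done on the day of discharge (footnote aa), inside the limit. Not affected.
- In hospital and drawn on Day 27 or 28: inside the limit. Not affected.
- In hospital with the only post-dose antibody draw on Day 29: affected.

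**Step 3: what happens to an affected participant.**

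| Output | Result under the literal text |
|---|---|
| Immunogenicity set (SAP 2.2.6) | Included |
| Positive/negative table | Excluded: no sample by study Day 28 |
| Listing of positives | Absent, even if positive |
| Concentrations by antibody status | Undefined |

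**Step 4: discharge after Day 28.** Protocol Appendix 3 marks the pharmacology sample for discharge up to Day 28. It leaves the columns for continued stay after Day 28 and for discharge after Day 28 empty. In the Schedule of Activities, footnote cc (weekly blood sampling after Day 28) is not attached to the pharmacology row. The endpoint therefore refers to a sample that the schedule does not provide.

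**Step 5: size.** Loss = n × h × w, with n = 74 critical sirukumab participants (SAP 1.4). Here h is the share still in hospital and sampled around Day 28, and w is the share of those drawn on Day 29. The documents give neither h nor w; both are assumptions. A value of w = 1/3 means draws spread evenly over the three days.

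| h | w | Loss of 74 | Share |
|---|---|---|---|
| 10% | 10% | 74 × 0.10 × 0.10 = 0.7 | 1.0% |
| 25% | 20% | 74 × 0.25 × 0.20 = 3.7 | 5.0% |
| 40% | 1/3 | 74 × 0.40 × 1/3 = 9.9 | 13.3% |

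For severe and critical participants together, n is about 74 + (2/3 × 100) = 141, taking the roughly 100 severe participants as split 2:1. The same three settings give 1.4, 7.0 and 18.8.

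**Step 6: expected positives among those lost.** Earlier IV studies (Protocol 2.1.1) found 0/31, 0/32 and 1/20, that is 1/83 = 1.2%. At that rate the loss of 0.7 to 9.9 participants carries 0.7 × 0.012 = 0.01 to 9.9 × 0.012 = 0.12 positives. The rate is only a rough guide: the single positive arose under repeated 10 mg/kg dosing, and the single-dose study had none.

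**The case against.** The strongest reply is that Day 28 in SAP 8.3.2 means the nominal visit. The SAP says it is to be read with the protocol, SAP 2.1.1 ends the treatment phase at the Day 28 visit, and Protocol 9.4.7 refers to the Day 28 sample. A programmer working that way would include a Day 29 draw. This reading is possible, but it is not what the text says. SAP 8.3.2 names study Day 28, SAP 2.3 ties study days to the dose date, and where the SAP wants a window it writes one. Two programmers could produce different tables from the same text, which is reason enough to settle it.

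A second reply also stands: Days 26 to 30 in SAP 7.2 is wider than the protocol's own allowance, and the Day 31 limit for viral load rests on a different window. They show that the SAP recognises windows, not that either should be copied here.

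A reader might infer several stronger things that the documents do not support:
- *Long-stay participants in general lose their result.* Everyone in hospital at Day 28 is due a draw, and it counts if taken on Day 27 or 28.
- *Affected participants are called negative.* That rests on half a sentence. SAP 8.3.2 adds in parentheses that a negative participant must be negative all the way through Day 28, which someone with no result cannot meet.
- *Incidence is biased downward.* Excluded participants leave both numerator and denominator. Bias would need Day 29 draws to be positive more often than draws one or two days earlier, and nothing shows that.
- *Samples at later discharge are discarded.* None is scheduled (step 4).
- *A lost positive is likely.* Step 6 puts the expected number at about 0.1 or less.

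**Conclusion.** The point holds in limited form. Read literally, SAP 8.3.2 drops a protocol-compliant Day 29 antibody result from participants whose only post-dose sample it is, and leaves their antibody status undefined in the concentration displays. The loss is about 1 to 10 of 74 critical sirukumab participants (1.0% to 13.3%). That range depends wholly on the assumed shares still in hospital (10–40%) and drawn on Day 29 (10–33%). The consequence is some loss of precision on an exploratory endpoint that is only described, with no formal test in 8.3.2 and no direction of bias shown. The mismatch between the endpoint's discharge wording and Appendix 3 is a separate inconsistency. This is a minor correction, worth making because the samples have already been drawn.

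**What to change.** In SAP 8.3.2, replace each limit at Day 28 with: *through the nominal Day 28 sample, including draws within the protocol window (at least through study Day 29)*. Apply it to the definitions of positive and negative, the results table, the listing, and the concentration tables and plots by antibody status. State that participants with no evaluable post-dose sample are missing, not negative.

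Separately, reconcile the endpoint's reference to discharge after Day 28 (Protocol 3, SAP 1.1) with Protocol Appendix 3, which schedules no pharmacology sample then. State that any such sample will be included if one was obtained.

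The cost is SAP wording and a small programming change. The window change needs no new samples.

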9 SAFETY

All safety analyses will be performed on the AST and Primary analysis sets.

The safety assessments to be evaluated include AEs, clinical laboratory tests, vital signs, and electrocardiogram (ECG).

Deaths during the study are evaluated as an efficacy endpoint.

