In addition, an IA was performed by the sponsor on the primary endpoint when approximately 20% of the planned number of participants with confirmed severe and critical COVID-19 disease had reached Day 28 or discontinued earlier (see Synopsis subsection *Interim Analysis* for more details). Results have been discussed with the DMC.

The above DMC set-up and non-binding futility criteria have been implemented in the study for the participants with confirmed severe or critical COVID-19 disease. No additional non-binding futility analyses are planned for the participants with confirmed critical COVID-19 disease in the study.

The efficacy endpoints will be analyzed on the Intent-to-Treat- (ITT) and by randomized treatment. The ITT set consists of all participants who were randomized and treated. These analyses will be performed in the participants with confirmed (a) critical and (b) severe and critical COVID-19 disease.

All safety analyses will be made on the Safety Population. The safety population, consisting of all participants who received study drug, will be analyzed by actual treatment. These analyses will be performed in the participants with confirmed (a) critical and (b) severe and critical COVID-19 disease.

For all participants who receive study drug descriptive statistics will be provided. All demographic characteristics (eg, age, race, ethnicity, height, body weight, body mass index) and other initial participant characteristics (eg, medical and surgical history, concomitant diseases) will be tabulated and analyzed descriptively.

Subgroup analyses will be performed based on the stratification factors (age [<65 and ≥ 65 years of age] and use of invasive mechanical ventilation [yes/no]) and a selection of the major baseline parameters.

Sample Size Determination

The study was targeted to enroll 270 participants with confirmed severe or critical COVID-19 disease in a 2:1 manner, with approximately 180 participants in the sirukumab treatment arm and approximately 90 participants in the control arm. However, based on the rapidly evolving space of COVID-19 therapeutics focusing on the highly impacted population of critical patients together with the results from the interim analysis, the study population is being limited with protocol amendment 5 to a subset of the currently eligible population, ie, those with confirmed critical COVID-19 disease.

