9.3. Populations for Analysis Sets

For purposes of analysis, the following populations are defined:

The efficacy endpoints will be analyzed on the Intent-to-Treat (ITT) and by randomized treatment. The ITT set consists of all participants who were randomized and treated.

The primary and key secondary analyses will be tested on the participants with confirmed critical COVID-19 disease.

All safety endpoints will be evaluated on the Safety Population which consists of all randomized participants who received study intervention and will be analyzed by actual treatment.

Pharmacokinetic data will be evaluated on participants in the ITT set who received sirukumab.

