2.2.3 Primary Analysis Set

The Primary analysis set consists of all participants in the ITT analysis set with confirmed critical COVID-19 disease defined as score of 4 or 5 on the CRS scale at baseline. For more details on CRS score please refer to Section 5: Efficacy. Treatment groups as randomized will be used for the analysis using this analysis set (Primary analysis set as Randomized).

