2.2.4 All Subjects Treated (AST) Analysis Set

The AST analysis set consists of all participants who received the study drug. This analysis set will be used to evaluate the safety of drug, using the actual treatment received by a participant (AST analysis set as Treated)

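### SAP section 9 analyses safety in critical participants on the as-randomised Primary set, whereas the protocol requires safety by actual treatment

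*SAP*

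**What the plan says.** **Protocol.** Section 9.3 evaluates safety on the Safety Population, "which consists of all randomized participants who received study intervention and will be analyzed by actual treatment". The Synopsis (Statistical Methods) gives the same rule: "The safety population, consisting of all participants who received study drug, will be analyzed by actual treatment". The sentence after it says that these analyses are done in (a) critical and (b) severe and critical disease. Section 9.4.6 repeats both populations for safety.

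**SAP.** Section 9 states: "All safety analyses will be performed on the AST and Primary analysis sets". Section 2.2.4 defines AST as everyone who received study drug, grouped by treatment received, and names it as the set for evaluating safety. Section 2.2.3 defines the Primary set as "all participants in the ITT analysis set with confirmed critical COVID-19 disease", meaning baseline CRS 4 or 5, and adds: "Treatment groups as randomized will be used for the analysis using this analysis set". The parent ITT set (2.2.2) is assigned to efficacy, subject information and virology. Safety is not among its stated uses.

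**The concern.** The protocol has one grouping rule for safety and two populations to which it applies. The SAP follows the rule for the combined population through AST. For critical disease it uses an efficacy set with the opposite rule. The two sets of safety tables would then group the same people differently whenever received and assigned treatment disagree.

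Safety in critical disease is a stated secondary objective. It covers serious and related adverse events, severe infections, neutropenia and lymphocytopenia, and raised ALT with bilirubin. A dosing error is possible: bags are prepared at site, and placebo is a locally supplied dextrose bag with nothing added (Protocol 6.1). The SAP itself plans a listing of actual against randomised treatment (4.4).

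**Working it through.** **Definition check**

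| Safety population in the protocol | Grouping in the protocol | Set in SAP section 9 | Grouping in the SAP |
|---|---|---|---|
| Severe or critical | Actual treatment | AST (2.2.4) | As treated |
| Critical | Actual treatment | Primary (2.2.3) | As randomised |

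The second row conflicts. For randomised participants, the Primary set and the critical part of AST contain the same people. Only the arm under which each is counted can differ.

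**Size**

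No figure stated in the plan is in dispute. Inputs:

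- Planned critical cohort: 111 at 2:1, so 111 × 2/3 = 74 sirukumab and 111 × 1/3 = 37 control (Protocol 9.2).
- Assumed, because the documents give no adverse event rates: the same background rate in both arms, 20% or 40%, rounded to whole participants.
- Assumed: one participant received the other arm's treatment and had the event.

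Formula: change = (as-randomised risk difference) − (as-treated risk difference), with difference = sirukumab minus placebo.

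| Error | Background rate | As treated | As randomised | Change (points) |
|---|---|---|---|---|
| Assigned placebo, received sirukumab | 20% | 16/75 − 7/36 = +1.9 | 15/74 − 8/37 = −1.4 | −3.2 |
| Assigned placebo, received sirukumab | 40% | 31/75 − 14/36 = +2.4 | 30/74 − 15/37 = 0.0 | −2.4 |
| Assigned sirukumab, received placebo | 20% | 15/73 − 8/38 = −0.5 | 16/74 − 7/37 = +2.7 | +3.2 |
| Assigned sirukumab, received placebo | 40% | 29/73 − 16/38 = −2.4 | 30/74 − 15/37 = 0.0 | +2.4 |

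One such participant therefore changes the difference by 2.4 to 3.2 points. On the same assumptions, two change it by 4.7 to 6.4 and three by 6.9 to 9.5. In the first row the sign reverses. With no misdosing the change is 0.

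**The case against.** Much of the as-treated information on critical participants is already planned. SAP 9.1.3 tabulates serious events, events of special interest, related events, grade 3 or higher events and events leading to death by baseline CRS, including 4 and 5 separately. Section 9.1.3 does not name the set. However, a row for CRS 3 or below can only be filled from AST, because the Primary set holds only CRS 4 and 5. Adding the AST rows for CRS 4 and CRS 5 gives as-treated counts for the whole critical cohort. Table 2 of the SAP adds selected laboratory results. There are also controls against error: the IWRS matches a kit to participants on active treatment (Protocol 6.3), administration is documented (Protocol 6.2), and SAP 4.4 lists actual against randomised treatment, so a reader could see any mismatch. Adverse events are not formally tested, and deaths are evaluated as an efficacy endpoint.

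All of this stands, and it limits the consequence. It does not supply an as-treated critical-cohort version of the overall system organ class and preferred term tables, vital signs, ECG or the laboratory tests not selected for subgrouping. A listing does not change how tables are grouped. The check in SAP 4.1 applies only when more than 5 participants differ in allocation between ITT and AST, and it adds only disposition and baseline tables. SAP section 1 says the SAP is read together with the protocol, but 2.2.3 is specific and a programmer would follow it.

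Three stronger readings are tempting, and the documents do not support them.

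- *A participant treated without being randomised is wrongly lost from critical safety.* SAP 4.3 foresees that category, and such a person would be in AST but not in the Primary set. But Protocol 9.3 limits the Safety Population to randomised participants, while the Synopsis includes everyone who received study drug. The protocol disagrees with itself, so this is not a clear SAP departure. Baseline CRS is also tied to the randomisation request (SAP 5.2.1), so such a person has no defined baseline category.
- *Biomarkers (SAP 7.1) need the same change.* They also use AST and Primary, but the protocol's actual-treatment rule concerns safety.
- *Each misdosed participant shifts the arms by 1/37 = 2.7 and 1/74 = 1.4 points in opposite directions, about 4.1 in total.* This ignores the change in both denominators when someone moves arm. In the first row of the size table the control rate moves by 2.2 points and the sirukumab rate by 1.1, or 3.2 in total before rounding.

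**Conclusion.** The conflict is real and confined to the critical-only safety outputs. The AST outputs follow the protocol. A reader might infer that events have been or will be charged to the wrong drug. The documents do not support that: they report no misdosing, and without it the tables are the same under either grouping.

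If misdosing occurs, the effect is about 2.4 to 3.2 points of risk difference per misdosed participant with an event. This rests on the planned 74 to 37 split, an assumed background rate of 20% to 40% that is equal in both arms, and the event having occurred in the misdosed participant. The adverse event tables by CRS and the listing in SAP 4.4 reduce the practical harm. This is a minor point, worth making because the SAP departs from an explicit protocol rule and the correction is easy.

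**What to change.** In SAP section 9, replace the Primary analysis set with the AST analysis set restricted to baseline CRS 4 or 5, analysed as treated. This applies the protocol's rule to both safety populations and makes the two sets of tables comparable.

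The cost is one line in the SAP, with no new data. If every treated critical participant was randomised and received the assigned treatment, the tables do not change.
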